1.1 Lay Summary

Pneumothorax (a collapsed lung) occurs when air leaks from the lung and accumulates between the chest wall and the lung, resulting in partial lung collapse. The build-up of air may impair diaphragm function (the muscle that helps us breathe). The mechanism of breathlessness in pneumothorax is unclear, and symptoms can vary between patients. Some patients present with minimal or absent symptoms, whilst others experience distressing breathlessness and pain. Sometimes tubes may need to be inserted between the ribs to drain the collected air and help the lung reinflate, and occasionally surgery is required to stop the leak.

Currently, the effect of the accumulated air in the pleural space and its association with diaphragmatic function and symptoms of breathlessness is not well understood. Bendopnoea (breathlessness when bending forward) is an evolving clinical symptom that has been demonstrated as clinically useful in some heart and lung conditions. Whether bendopnoea is present in patients with pneumothorax, and its potential clinical usefulness has not yet been investigated.

The PASE study is a pilot study to explore the incidence and clinical relevance of bendopnoea in patients with pneumothorax and may provide better understanding of breathlessness in pneumothorax.

2 Rationale / Background

Pneumothorax is a condition characterised by the presence of air in the pleural space between the lung and chest wall (1). This abnormal accumulation of air can cause partial or complete collapse of the lung, and the patient can experience breathlessness and chest pain (2, 3).

Pneumothorax can be classified as spontaneous or traumatic (including from medical procedures). Bendopnoea is a simple and safe bedside test that requires patients to bend forward and report symptoms of breathlessness. It does not require the use of any equipment or specific resources and can be completed within 60 seconds, therefore the test can be easily replicated during routine assessments in all settings.

In patients with pneumothoraxes, the level of breathlessness varies amongst patients and the precise mechanism of breathlessness in pneumothorax remains unknown. In contrast, breathlessness in patients with pleural effusion is now linked with diaphragmatic dysfunction due to presence of pleural fluid. Whether that holds true for pleural air in pneumothorax is also unknown. Bendopnoea is emerging as a clinically useful symptom related to patient outcomes in many cardiorespiratory diseases, however, it has not yet been explored in pleural disorders. Our literature review found bendopnoea is a clinical biomarker in patients with advanced heart failure (HF) (7, 8) and with pulmonary arterial hypertension (PAH) (9) that is prognosis (7, 8), worse functional capacity (9), haemodynamic characteristics (9) and right ventricular function (9).

The incidence of bendopnoea has not yet been reported in patients with pneumothorax (Aim 1), including the correlation of bendopnoea with pain, breathlessness, size of pneumothorax and respiratory physiological parameters (Aim 2). In the context of pneumothorax, the clinical usefulness of bendopnoea as a predictor of outcome is yet to be explored (Aim 3).

3 Trial Aims / Objectives / Hypotheses

The PASE study will explore the incidence of breathlessness on bending forward (bendopnoea) in patients with pneumothorax and whether this is associated with symptoms, size of pneumothorax, physiological parameters and the clinical outcome.

We hypothesize that bendopnoea:

- 1. Is prevalent in individuals with pneumothorax
 - a) Associated with higher levels of breathlessness,
 - b) Reflect size and types of pneumothoraxes, and
 - c) Correlated with clinical outcome (i.e., response to drainage/lung reinflation).

Study Aims and Outcomes:

In a prospectively recruited unbiased/unselected cross-sectional cohort of patients with pneumothorax, this study will explore the:

- 1. Incidence of bendopnoea in this population,
 - *a*. Correlation of the associated symptoms (pain and breathlessness) to the severity of bendopnoea and the size of pneumothorax; and
 - b. Correlation with clinical outcome (i.e., response to drainage/lung reinflation).
- 2. Pathophysiological basis of bendopnoea by:
 - *a.* Determining the relationship of bendopnoea with breathlessness scores, pain scores and physiological parameters (e.g. oxygen saturations).

The above will be performed in all patients at baseline and for patients where air drainage is indicated as per standard care, once the drain is removed.

4 Trial Design

4.1 Study Endpoints

Overall:

- 1. To determine whether bendopnoea is present in patients with pneumothorax,
- To determine whether bendopnoea is associated with clinical symptoms (pain and breathlessness), the size of pneumothorax and respiratory physiological parameters; and
- 3. To determine whether bendopnoea is correlated with clinical outcome (i.e., response to drainage/lung reinflation).

4.2 Type of design

PASE is a multi-centre prospective study.

4.3 Study Duration

The study will enrol participants for a period of 24 months. This is based on the number of potentially suitable participants seen in the recruiting centres (\sim 2/month).

4.4 Trial Termination

Early trial termination may occur for the following reasons,

- a. The Data Safety and Monitoring Committee has significant concerns and advise early trial termination. This can be preceded by a period of no enrolment at the site whilst investigation of the safety issues is conducted.
- b. Alterations in accepted clinical practice making the continuation of the clinical trial untenable.

4.5 Data identification

Each study patient will have a unique study identification code created following informed consent which will comprise their first name and last name initials and a consecutive number generated at the time of randomisation. Study participants will have individual trial notes created separate to the participant's medical records. These will be kept in a secure (locked) filing cabinet in a locked office in the SCGH Respiratory Department.

5 Source and Selection of Participants

5.1 Source of Participants

This study will enrol 50 consecutive eligible patients with pneumothorax from the pleural service of Australian centres. A screening log will be maintained. Patients who require drainage/lung reinflation as part of their clinical care will be assessed before and after reinflation. All participants will receive standard care for their conditions as per their treating clinicians. From the time of signing consent, participants will remain in the study for 3 months.

5.2 Participant inclusion criteria

• In- and out-patients referred for assessment of a unilateral spontaneous (primary or secondary) pneumothorax or iatrogenic pneumothorax.

5.3 Participant exclusion criteria

- Pneumothorax with a concurrent pleural effusion > 1cm in size
- Hemodynamically unstable (systolic blood pressure of <90 mmHg, heart rate in beats per minute greater than or equal to systolic blood pressure in mmHg, respiratory rate of >30 breaths per minute, and Spo2 of <90% on room air)
- Age <18 years
- Mechanical limitations in bending forward (*e.g.*, spinal conditions or large abdominal mass)
- Pregnancy/lactation
- Inability to consent and/or comply with protocol

5.4 Participant withdrawal criteria

Participants can withdraw at any time from the study and do not need to provide a reason. We will retain all participant data up until the time of withdrawal as outlined in the PICF. There may be reasons for the site PI to decide to withdraw a participant from the study. This could be due to inability to comply with the study protocol such as attending study visits or for other compliance issues. A participant may also be withdrawn in their best interests. In all cases, the study withdrawal form will be completed and a copy submitted to the lead site. Withdrawn participants will not be replaced. If considered clinically necessary, withdrawn participants will be asked to return to clinic for safety follow-up appointment(s).

6 Treatment of Participants

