8.3 Selection of participants for analyses

All patients who fulfil the criteria and consent for the study will be included in the analyses, to minimise/exclude selection bias. Our team includes experienced biostatistician [name] (University of Western Australia) for study planning and data analyses.

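### Section 5.4 lets the site investigator withdraw participants for missed visits and provides no outcome collection afterwards, so response to drainage is exposed to avoidable and possibly selective loss

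*Protocol*

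**What the plan says.** Section 5.4 covers withdrawal by the participant and then by the investigator: "There may be reasons for the site PI to decide to withdraw a participant from the study". It continues: "This could be due to inability to comply with the study protocol such as attending study visits or for other compliance issues". Withdrawal in the participant's best interests is listed as a separate reason.

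On data, the same section says: "We will retain all participant data up until the time of withdrawal as outlined in the PICF". Later contact is limited to safety appointments where clinically needed, and "Withdrawn participants will not be replaced".

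Section 8.3 defines the analysis population: "All patients who fulfil the criteria and consent for the study will be included in the analyses, to minimise/exclude selection bias".

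Schedule 1 in the appendices has two visits: Day 0, and a second once the drain is removed. Section 6.1 confirms that only patients who go on to drainage have the second assessment. Section 5.1 keeps participants in the study for 3 months from consent. Section 8.2 plans to estimate the change from baseline to after the intervention, and to model the correlation of bendopnoea with clinical outcome. Section 4.1 describes that outcome as response to drainage or lung reinflation.

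**The concern.** Failing to attend is a reason for missing data. Section 5.4 also makes it a reason to end participation. The ground is discretionary and its second half, covering other compliance problems, is undefined, so sites in a multi-centre study may apply it differently.

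Whether a patient attends a visit triggered by drain removal may depend on how drainage went. If such patients are withdrawn and nothing more is collected, those left in the analysis of response to drainage are no longer the unselected cohort that section 3 describes. The study aims for 50 participants, the drained subset is smaller, and withdrawals are not replaced, so each lost outcome counts. An analysis plan cannot recover data that were never collected, so the matter belongs in the protocol and the consent form.

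**Working it through.** The protocol gives no withdrawal rate, drained share or response rate, so there is no figure of its own to reproduce. The check is mainly a comparison of sections, followed by an illustration of scale.

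**1. Whom the ground can reach.** Schedule 1 has no visit after Day 0 for undrained patients. A drained patient can miss only Visit 2. Non-attendance as a ground therefore acts on the drained subset.

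**2. What withdrawal adds to a missed visit.**

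| Item | Visit 2 missed, participant kept | Visit 2 missed, participant withdrawn |
|---|---|---|
| Day 0 bendopnoea, VAS, size, physiology | held | held |
| VAS and bending test at the planned time | lost | lost |
| Late Visit 2 measurement | possible | closed off |
| Response to drainage or reinflation, from records | obtainable to 3 months | no provision to collect |

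Only the last two rows are due to the withdrawal rule. The last row is avoidable: section 6.1 already draws on case notes, section 8.4.1 says medical records are available to the investigator, and section 7.2 places drainage and surgery within standard care, so the outcome arises without a study visit.

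**3. Scale of loss (assumed inputs).** Take 50 participants (section 8.1). Assume 40–80% are drained, 5–20% of those are withdrawn before Visit 2, response is yes/no, and about 60% of those observed respond.

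- Drained: 50 × 0.4 = 20 to 50 × 0.8 = 40.
- Lost: 20 × 0.05 = 1 to 40 × 0.20 = 8.
- Bounds = (responders seen)/n to (responders seen + lost)/n, with width lost/n.
- n = 20, lost 1, 11 of 19 respond: 11/20 = 55.0% to 12/20 = 60.0%.
- n = 30, lost 6, 14 of 24 respond: 14/30 = 46.7% to 20/30 = 66.7%.
- n = 40, lost 8, 19 of 32 respond: 19/40 = 47.5% to 27/40 = 67.5%.

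The bounds are thus 5 to 20 points wide in these cases.

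**4. Effect of selective loss (assumed inputs).** Let the true response be p = 0.60, with loss a in responders and b in non-responders. The observed proportion is p(1−a) / [p(1−a) + (1−p)(1−b)].

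- a = 0.20, b = 0.05: 0.48/(0.48 + 0.38) = 55.8%.
- a = 0.30, b = 0.05: 0.42/(0.42 + 0.38) = 52.5%.
- a = 0.05, b = 0.20: 0.57/(0.57 + 0.32) = 64.0%.
- a = 0.05, b = 0.30: 0.57/(0.57 + 0.28) = 67.1%.
- a = b = 0.10: 0.54/(0.54 + 0.36) = 60.0%, no bias.

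These figures assume that every loss comes from withdrawal with no outcome taken from the record. Where response was already documented before withdrawal, the effect is smaller.

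**5. The association.** Loss that depends on response alone moves the response proportion but leaves the odds ratio between baseline bendopnoea and response unchanged. Distorting the odds ratio needs loss that depends on bendopnoea and response jointly. Other measures, such as a risk difference or a correlation coefficient, can shift in either case.

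**The case against.** The strongest reply is that little is lost. The rule is permissive, and nothing turns one missed visit into withdrawal. The first aim, bendopnoea at presentation and its relation to symptoms, size and physiology, rests on Day 0 data, which are retained. Visit 2 scores are lost by the absence itself, so the rule does not cause the gap in the before-after change, except where a late measurement would have been possible. All of this stands.

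A second reply is that an end to data collection is not stated. The retention sentence comes before investigator withdrawal is introduced and defers to the PICF, which is not available to this review. This stands in part. The end of collection is an inference from retention up to withdrawal and from safety being the only later contact. The protocol still makes no provision for outcome after investigator withdrawal.

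Four stronger readings may tempt a reader, and the protocol does not support them:

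- *Section 5.4 contradicts section 8.3.* It does not. Withdrawn patients are not excluded and can be analysed with the data held.
- *Every post-baseline endpoint is defeated.* The table above shows a narrower loss.
- *Recurrence is lost.* The protocol does not name recurrence as an outcome.
- *The bias is 2–6 points.* That comes from multiplying an assumed 10–20% withdrawn by an assumed 20–30 point difference in response (0.1 × 0.2 = 0.02 to 0.2 × 0.3 = 0.06). It charges all the loss to the withdrawal rule.

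Non-replacement costs precision but is not itself a source of selection bias. How missing Visit 2 values are analysed may properly be left to the SAP.

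**Conclusion.** The point holds in a limited form. Section 5.4 allows discretionary, possibly outcome-related withdrawal for non-attendance or unspecified compliance problems, with no provision for outcome afterwards. This works against the purpose stated in section 8.3 for the analysis of bendopnoea against response to drainage or reinflation. The avoidable part is late Visit 2 measurement and the clinical outcome in the record.

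Selective loss is a risk and not a certainty. Neither its size nor its direction follows from the protocol, and the percentages above rest wholly on assumed drained shares, loss rates and response. The conclusion also assumes that the PICF does not already provide for record follow-up after investigator withdrawal. This is a cheap improvement to a stated rule and does not call the study's main aim into question.

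**What to change.** In section 5.4, remove non-attendance and the open-ended compliance wording as grounds for investigator withdrawal from the study. State instead that:

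- a missed visit is recorded as missing and the participant stays in the study;
- a late Visit 2 assessment may be done, with its date recorded;
- response to drainage or lung reinflation is taken from the medical record up to 3 months from consent, unless the participant withdraws consent to data use.

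Leave withdrawal in the participant's best interests, safety follow-up and clinical care as they are. Align the PICF with this wording.

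The cost is an amendment to the protocol and PICF wording, with the ethics review that this needs, and a short chart review for a few patients.

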6.1 Intervention

The following parameters will be assessed using a range of validated tools for all patients

- 1. At baseline (pre drainage/lung reinflation) and,
- 2. For those proceeding to drainage, once the drain is removed.

Bendopnoea is assessed:

- 1. In a qualitative manner (as modified from Baeza-Trinidad et al (11)) with the following question:
 - a. "Since the onset of your symptoms, how has shortness of breath when bending forward impacted your day-to-day activities?"
 - i. No limitation: I was not troubled by breathlessness when bending forward
 - Mild: I felt breathless when bending forward and performing an activity (e.g., tying shoelaces) but can still perform activities without limitation or rest.
 - iii. Moderate: I had to stop and take breaks from bending forward to complete what I wished to do (e.g. I have to bend down several times to complete tying the laces of both shoes).
 - iv. Severe: I was too breathless to bend forward
 - b. After the air drainage procedure, the question will be phrased: "since the procedure, how does shortness of breath when bending forward impact your day-to-day activities?"
- 2. With objective testing, as per published studies (9, 11, 12):
 - a. Patient sitting in a chair is instructed to bend forward at the waist and aim to touch his/her ankles and maintain this position for up to 60 seconds. Patient will inform the investigator as soon as breathlessness occurs, and the time of onset of bendopnoea recorded.
 - b. Bendopnoea is recorded as:
 - i. Time to breathlessness, and
 - ii. Present or absent during the test.

Degree of breathlessness and impairment on functional activities:

Breathlessness will be measured using a 100mm visual analogue scale (VAS) anchored by "no shortness of breath at all" and "maximum shortness of breath" (13). VAS scores have been used previously to measure breathlessness in this population (14). The mean of the VAS scores measured by two independent researchers will be documented.

Degree of pain and impairment on functional activities:

Pain will be measured using a 100mm visual analogue scale (VAS) anchored by "no pain" and "worst pain" (15). The mean of the VAS scores measured by two independent researchers will be documented.

Patient characteristics Breathlessness can be a result of concurrent illnesses (e.g., heart failure, COPD etc) and intrathoracic (e.g., pulmonary emboli) or extrathoracic factors (e.g., muscle wasting) which will be captured from case notes. Height, weight and body mass index will be recorded. Cardio-pulmonary status (respiratory and heart rates, blood pressure and oxygen saturation) and the aetiology of the pneumothorax will be recorded.

Pneumothorax Characteristics The size of the pneumothorax will be measured on standard erect PA inspiration chest radiographs (CXR) with the Light Index (1) and Collins Method (16). The Light Index measures the average diameter of the lung and the hemithorax, cubing these diameters, and finding the rations (1) whereas the Collins Method calculates the 'sum of interpleural distances' which estimates the pneumothorax size (16).

7 Assessment of Safety

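### Section 6.1 does not define how the chair test is scored in a patient who is already breathless when seated, and the two possible codings bias the results in opposite directions

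*Protocol*

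**What the plan says.** Protocol section 6.1 describes the objective test, which lasts at most one minute: "Patient sitting in a chair is instructed to bend forward at the waist and aim to touch his/her ankles and maintain this position". The reporting rule is: "Patient will inform the investigator as soon as breathlessness occurs, and the time of onset of bendopnoea recorded". Two results are recorded, the time to breathlessness and "Present or absent during the test". The test is said to follow three published studies (references 9, 11 and 12), but no rule of theirs for resting breathlessness is restated.

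The same section adds a four-grade question on breathlessness when bending, and a 100 mm breathlessness VAS. Schedule 1 places the VAS, the question and the chair test at both visits. Neither place states the posture for the VAS or its timing relative to the bend.

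The lay summary (1.1) says that some patients have few or no symptoms, "whilst others experience distressing breathlessness and pain". Section 5.3 excludes haemodynamic instability but not breathlessness at rest. Section 3 hypothesises that bendopnoea is "Associated with higher levels of breathlessness" (Hypothesis 1a), and Aim 2a relates bendopnoea to the breathlessness scores. Section 8.2 will also estimate the change from baseline to after the intervention.

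**The concern.** A patient who is breathless while sitting upright can enter the study, and the test has no stated result for that patient. Two codings fit the wording:

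- **Present, onset 0 s.** The patient is breathless while bent, so the test is positive.
- **Absent, no onset.** Nothing began during the bend, so the test is negative.

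These lie at opposite ends of both recorded scales. Under the first coding, resting dyspnoea enters the bendopnoea variable and is then correlated with a breathlessness score. Under the second, the most breathless patients are recorded as free of bendopnoea. The study is multi-centre, so sites may differ.

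The before-after comparison is exposed too. Take a patient with resting dyspnoea that settles after drainage and no bend-provoked breathlessness at either visit. The first coding records present then absent, which looks like resolved bendopnoea. If the patient instead has bend-provoked breathlessness at both visits, the second coding records absent then present, which looks like bendopnoea appearing after drainage.

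This is a bedside definition. Analysis cannot recover a seated state that was not recorded.

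**Working it through.** The protocol states no figure on this point, so there is none to reproduce. The check asks how large an association each coding creates when none exists.

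**Inputs.** From the protocol: n = 50 (8.1) and the scoring rule (6.1). Assumed, because the documents do not give them: a share *f* breathless at rest; a probability *p* of bend-provoked breathlessness, independent of resting breathlessness; VAS mean 45 mm (SD 20) if breathless at rest and 12 mm (SD 10) if not.

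**Formulas.** VAS variance: V = 400f + 100(1 - f) + 33²·f(1 - f), where 33 = 45 - 12.

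- Coded present: recorded prevalence q = f + (1 - f)p; mean VAS difference (present minus absent) d = 33f/q.
- Coded absent: q = (1 - f)p; d = -33f/(1 - q).
- Both: r = d·√[q(1 - q)]/√V.

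**Worked case, f = 0.35, p = 0.30.** V = 140 + 65 + 1089 × 0.2275 = 452.7, so √V = 21.28.

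- Coded present: q = 0.35 + 0.65 × 0.30 = 0.545; d = 11.55/0.545 = 21.2 mm; r = 21.2 × 0.498/21.28 = +0.50.
- Coded absent: q = 0.65 × 0.30 = 0.195; d = -11.55/0.805 = -14.3 mm; r = -14.3 × 0.396/21.28 = -0.27.

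True prevalence is 30% and true r is 0. Recorded prevalence is 54.5% or 19.5%.

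**Range.** Spurious r, coded present / coded absent:

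| f | p = 0.20 | p = 0.30 | p = 0.40 |
|---|---|---|---|
| 0.05 | 0.23 / -0.06 | 0.18 / -0.08 | 0.15 / -0.10 |
| 0.10 | 0.35 / -0.10 | 0.29 / -0.13 | 0.24 / -0.16 |
| 0.20 | 0.48 / -0.16 | 0.41 / -0.20 | 0.35 / -0.25 |
| 0.35 | 0.56 / -0.21 | 0.50 / -0.27 | 0.43 / -0.32 |
| 0.50 | 0.59 / -0.24 | 0.53 / -0.30 | 0.47 / -0.36 |

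**Simulation.** Studies of 50 patients with the worked-case inputs gave mean r of +0.50 and -0.27. A 5% test would call these significant in 99% and about 45% of studies, against 4-5% when only true bend-provoked breathlessness is scored. For coded present at p = 0.30, the share falls to 54% at f = 0.10 and 26% at f = 0.05.

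**Second model.** VAS was uniform on 10-90 mm if breathless at rest and 0-10 mm otherwise, with a Mann-Whitney test at 5%. For f from 0.2 to 0.6 and p of 0.2 or 0.4, coded present was significant in 66-100% of studies. With f = 0 the rate was about 5%. Scoring only new or worse breathlessness gave 4-5% throughout and returned the true prevalence.

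**The case against.** **The wording may already mean new breathlessness.** The words for occurrence and onset, in an instruction to a seated patient who then bends, can fairly be read as an event that begins during the bend. A reader might infer that the test counts any breathlessness and that Hypothesis 1a is therefore confirmed by construction. The text does not support that: it holds under one coding only, and under the other the bias runs against 1a. What stands is that the protocol does not choose, and even the new-onset reading leaves worsening of existing breathlessness unscored.

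**The cited studies may contain a rule.** They are not at hand, so it cannot be said that the trial has no rule. It can be said that the protocol writes out its own procedure without one.

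**The VAS at the same visit shows who is breathless.** This helps in part. But its posture and timing are not stated and it does not enter the scoring. Nor can 1a be adjusted for it, because the VAS is the variable that 1a tests.

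**The sizes are assumed.** This is correct. The lay summary describes pneumothorax in general and does not say how many enrolled patients are breathless at rest. Independence and uniform coding are also assumptions. The protocol sets no significance test, so the significance rates only give a sense of scale.

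**This is a pilot with a second bendopnoea measure.** That lowers the severity. The four-grade question does not compare with the resting state either, and the presence and correlates of bendopnoea are the pilot's stated endpoints.

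**Conclusion.** The point holds as an undefined result: section 6.1 does not say how a patient already breathless when seated is scored. Either coding biases prevalence, the VAS association and the before-after change, in opposite directions. A reader might go further and say these patients have no valid result; the documents show only that the result is not defined.

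Under the stated assumptions, with 5-50% breathless at rest and 20-40% true bendopnoea, the spurious correlation is about 0.15 to 0.59 if they are coded present and about -0.06 to -0.36 if coded absent. The direction under each coding does not depend on the share breathless at rest, but the size does. If almost no enrolled patient is breathless at rest, the effect is negligible.

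This should be fixed, but it does not invalidate the study: it is an observational pilot with a second measure of bendopnoea.

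**What to change.** In section 6.1 and Schedule 1:

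1. At both visits, immediately before the bend, record whether the seated patient is breathless. The existing breathlessness VAS, taken seated at that moment, would serve.
2. Define present as new breathlessness, or breathlessness that the patient reports as worse than when seated. Time that onset or worsening. Use the same wording at every site.
3. Flag patients breathless when seated. Report prevalence, the VAS association and the before-after change with and without them.

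The cost is one question, one CRF field and a sentence in the test definition, with no added visit or equipment. Compared with the present wording, recorded prevalence may move either way: in the worked case it would go to 30% from 54.5% if sites had coded these patients present, or from 19.5% if they had coded them absent.
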